### **C. Preliminary Studies/Progress Report**

Drs. [name] and [name] have used smartphones in 9 studies to collect EMA data for up to 6 months and influence health behavior in high-risk samples, including homeless (e.g., 1R01MD010733-01A1; PI [name]) and other socioeconomically disadvantaged adults (e.g., R01CA197314-01; PI [name]). In *Project Prevail*, EMA data were collected from smokers seeking treatment at a safety-net hospital tobacco cessation clinic ( $N=146$ ). Participants completed 83% of all EMAs. Using just 6 EMA variables (i.e., urge, stress, cigarette availability, alcohol use, motivation to quit, proximity to others smoking), we created a smoking lapse risk estimator that identified 80% of all smoking lapses within 4 hours of the lapse (false positive rate = 17%; see a detailed description of the development of the risk estimator here). In another study, we developed the *Smart-T* app that includes on-demand features (e.g., tips on coping with stress) and incorporates the *Prevail* lapse risk estimator to deliver tailored messages based on a person's momentary risk for smoking lapse. We examined the feasibility of the *Smart-T* app among smokers recruited from an urban safety-net hospital tobacco cessation clinic ( $n=59$ ). In that study, socioeconomically disadvantaged participants completed 87% of all EMAs and received an intensive level of tailored smoking-cessation treatment messages (102 messages on average) over a 3-week intervention period. We found that the on demand app functions were used regularly and the app was well-liked (e.g., 97% would like to use the app in the future if they were to relapse, and 85% would refer their friends who smoke to use the app). Analyses of EMA data revealed that urges to smoke were significantly reduced when tailored urge messages were delivered by the app, as compared to instances where other types of messages were delivered ( $p<.001$ ). We also found reductions in stress ( $p=.021$ ) and cigarette availability ( $p<.001$ ) following tailored stress and cigarette availability messages, compared to other types of messages. A total of 20% of participants were biochemically confirmed abstinent 12 weeks post-quit, which is better than many interventions conducted with low SES smokers. Finally, [name] is completing a 3-armed pilot randomized

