constructs that are hypothesized to be related to smoking lapse (see Table 3). Three types of EMAs will be used: daily diary, random sampling, and event sampling. Random and daily diary EMAs will be prompted and initiated by the phone. The phone will ring and vibrate to cue these EMAs for 30-60 seconds. If the participant has not responded after 5 prompts, the EMA will be recorded as missed. Event sampling is initiated by participants. Participants are instructed to self-initiate "Record Cigarette" EMAs during the pre-quit period, and "Lapse" EMAs during the post-quit period. We expect random and event sampling EMAs to take approximately 30 seconds to complete and daily diary EMAs to take approximately 1-2 minutes to complete. All EMAs will be date and time stamped for future analyses.

**Daily diary.** Daily diary EMAs will be completed twice each day for the first 14 weeks of the study and once per day for the last 13 weeks of the study. The phone will initiate the morning daily diary 30 minutes after the participant's pre-set wake time (weeks 1-14) and questions ask about the previous day (e.g., "How many cigarettes did you smoke yesterday?" "Did you use marijuana yesterday?", and "Did you drink any alcohol yesterday?" If the participant answers "yes," he/she will be prompted to indicate the type and quantity of the alcohol/cigarettes that were consumed). In addition, participants will be asked each day if they experienced severe NRT side effects (the app will instruct participants to call 911 if they experience severe NRT side effects, and it will automatically send research staff an encrypted email to contact participants). For the entire 27 weeks of the study, the end of day daily diary will be completed 60 minutes before the

Alcohol Quantity and Frequency Questionnaire 	9		X	X	Cessation Motivation
Alcohol Quantity and Frequency Questionnaire 	9		X	X	Interaction with Smokers
Treatment Quality and Satisfaction Survey	19			X	Social setting/Location
Treatment Quality and Satisfaction Survey	19			X	Reasons for Lapse*
Treatment Improvement Interview 	18			X	Cigarette Reward Value*
Locator Form 	8		X		Lapse Warning Signs*
Financial Strain Questionnaire	9		X		Weekly EMA
MacArthur Major Discrimination	4		X		Pain
Modified Cigarette Evaluation Measure	12		X		Treatment Quality
Short Scale Anxiety Index	5		X	X	HRQoL
Religious Questionnaire	2		X		Readiness to Change

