Perceived Neighborhood Disorder and decay	15		X		Sleep
Collective Efficacy	10		X		Smoking Items
Informal Integration with Neighbors	3		X		Pandemic Stress Index
Fear & Mistrust	7		X		Covid Vaccine
Personal Victimization	3		X		
Perceptions of Mobile Phone Intervention Questionnaire	23		X		
Covid Vaccine	5		X	X	
Delay Discounting Task (TOAD)	10		X		
Time needed to complete assessment (minutes)	--	8	60	40	†Note: Daily Diary EMAs also contain all Random EMA items
Note. *Event EMA's only. Screen = Screening; Base = Baseline; 26-W = 26Week Post-Quit Follow-Up.					

participant's pre-set bedtime. If the participant does not respond to the daily diary assessments, they will be rescheduled (up to 2 times) 15 minutes later. A carbon monoxide test will be included as one component of this EMA 3 days each week. Participants will not receive credit for completing the end of day EMA if they do not complete the prompted iCO breath tests. Both the morning and end of day daily diary EMAs will include all random sampling items. Constructs that will be assessed are listed in Table 3 and actual EMA items are presented in the Appendix. Note: During one EMA each week, participants will be asked multiple questions about the usefulness of their app (see Appendix).

*Random sampling.* Participants will be prompted to complete random EMAs, scheduled to occur during each participant's normal waking hours, 3 times each day for 5 weeks (1 week pre-cessation and 4 weeks post-cessation) and 1 time per day for the next 9 weeks (week 6 through 14). Random sampling will not be conducted during weeks 15-27. EMA items will assess the 6 items used for the lapse risk estimator (i.e., urge to smoke, stress, recent alcohol use, interaction with other smokers, cessation motivation, and cigarette availability). Other relevant constructs will also be assessed during random sampling (e.g., recency of smoking, odds of smoking today; See Table 3 and Appendix).

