using linear mixed model (LMM) regression analyses employing a random intercept or slope parameter, as appropriate, and modeling the covariance structure for the repeated outcome measures, while accounting for baseline participant characteristics. Another analysis will look across all paired EMA scores within an individual and assign each individual a success percentage score based on the number of times their paired EMA scores decreased by at least one point on the Likert scale. For example in an individual that has 50 paired EMA scores for smoking urge, if 40 resulted in a decrease in urge, 5 resulted in no change, and 5 resulted in an increase in urge, the success percentage score would be 80% (40/50). Then we can compare the mean success percentage scores between treatment conditions using independent t-tests followed by regression analysis to account for baseline participant characteristics. Additional analyses will compare success percentage scores early versus late in the study to examine if the effectiveness of tailored messages change through time. Finally, we will examine the interaction between Smart-T message type and sex (and race) to identify potential differential effects on lapse risk factors.

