*Nicotine Withdrawal.* There is a strong likelihood that most study participants who quit smoking will experience some nicotine withdrawal symptoms, including anxiety, restlessness, anger, irritability, sadness, problems concentrating, appetite change and weight gain, insomnia, and decreased heart rate. Withdrawal symptoms are usually short-lived, with most symptoms abating within 1-2 weeks. Importantly, Drs. [name] and [name] are trained and experienced in addressing these issues as they emerge and the research team will be trained and supervised in the monitoring and addressing of psychological problems.

*Nicotine Replacement Therapy (NRT; Patch and Gum/Lozenge).* Nicotine patch and gum/lozenge are smoking cessation medications that are available over the counter and side effects (e.g., nausea, skin irritation) are generally mild. All participants will receive NRT. NRT has been shown to increase successful smoking cessation, and is currently offered via Quitline via mail in all but 5 states. Consistent with over-the-counter package labeling, participants will be offered up to 10 weeks of nicotine patches (i.e., label dosage recommendations will be followed) and up to 12 weeks of nicotine gum or lozenges (i.e., participants will receive a 4 week supply of NRT at the baseline visit and will be mailed NRT upon request for post-quit weeks 5-12). After 12 weeks, pharmacotherapy will be discontinued. Participants will be asked if they experienced NRT side effects each day via EMA. If/When participants report severe side effects, the app will suggest that the participant call 911. In addition, the app will automatically send an encrypted email to study staff when severe side effects are reported. Study staff will attempt to contact the participant to discuss these side effects.

*Alternative Treatments.* The consent form will explain that, rather than participating in this study, individuals may choose to enroll in the standard Tobacco Treatment Research Program (TTRP) which provides free smoking cessation medications and in-person, or phone-based smoking cessation counseling.

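### An early-versus-late comparison of message success across weeks 2-14 mixes real change with a doubled gap between paired EMAs from week 6 and, without a QuitGuide contrast, with the course of withdrawal

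*Combined protocol and SAP*

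**What the plan says.** Section E (Statistical Methods, Aim 2) forms consecutive EMA pairs in which the first EMA triggers a tailored message, and places them in weeks 2-14, at up to four pairs a day. Each participant then gets a success percentage, "based on the number of times their paired EMA scores decreased by at least one point on the Likert scale". After a between-condition comparison of mean scores comes the sentence at issue: "Additional analyses will compare success percentage scores early versus late in the study to examine if the effectiveness of tailored messages change through time". No cut-point between early and late is given, no contrast between conditions is stated for this comparison, and time between the two EMAs is not mentioned. The mixed models described just before it adjust for baseline characteristics only.

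The schedule is under Description of Study Measures. On diaries: "Daily diary EMAs will be completed twice each day for the first 14 weeks of the study". Random EMAs come "3 times each day for 5 weeks (1 week pre-cessation and 4 weeks post-cessation) and 1 time per day for the next 9 weeks", that is, through week 14. The Compensation paragraph confirms the totals: five prompts a day at first, then three in weeks 6-14. The morning diary comes 30 minutes after the set wake time and the evening diary 60 minutes before the set bedtime throughout weeks 1-14. All EMAs are date and time stamped.

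On withdrawal, section G says: "Withdrawal symptoms are usually short-lived, with most symptoms abating within 1-2 weeks".

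**The concern.** The score records whether a rating is lower at the next EMA. Moving that EMA further from the message changes what is measured, even if the message works exactly as before. The planned step-down does this at week 6, inside the window from which the pairs are drawn. A message of constant effectiveness could then look as if it wears off, or real waning could be hidden.

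There is a second source of drift. The quit date falls one week after baseline, so the first one to two weeks after quitting are study weeks 2-3, inside any early period. Unless the comparison is made against QuitGuide, a change in ratings that comes from withdrawal settling is mixed in with the message effect.

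At stake is the answer to a question that the plan asks explicitly: does the effectiveness of tailored messages change over time?

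**Working it through.** **1. The plan's own pair count.** Section E: 4 pairs a day x 91 days (weeks 2-14) = 364; 364 x 0.80 completion x 0.25 high risk = 72.8, which is the stated 73. It reproduces only if four pairs a day continue through week 14. The actual schedule gives 28 days x 4 = 112 pairs in weeks 2-5 and 63 days x 2 = 126 in weeks 6-14, 238 in all, and 238 x 0.80 x 0.25 = 47.6 high-risk pairs. The step-down was not carried into the Aim 2 arithmetic.

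**2. Gap between paired EMAs.** The two diaries fix both ends of the day, so mean within-day gap = (waking hours - 1.5) / (EMAs per day - 1). Waking hours are not in the documents; I assume 16, with range 14 to 18.

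| Waking hours | Weeks 2-5 (5 a day) | Weeks 6-14 (3 a day) | Ratio |
|---|---|---|---|
| 14 | 12.5/4 = 3.1 h | 12.5/2 = 6.25 h | 2.0 |
| 16 | 14.5/4 = 3.6 h | 14.5/2 = 7.25 h | 2.0 |
| 18 | 16.5/4 = 4.1 h | 16.5/2 = 8.25 h | 2.0 |

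The ratio does not depend on the length of the day. If a missed prompt is skipped and the next completed EMA that day is used (80% completion, simulated), it is 1.8 to 1.9. If overnight pairs counted, it would be (24/3)/(24/5) = 8.0/4.8 = 1.67.

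**3. Effect of the split.** Split at week 5/6: 100% of early pairs and 0% of late pairs are on the short-gap schedule. Split at weeks 2-8 versus 9-14: early has 112 + 42 = 154 pairs, of which 112/154 = 73% are short-gap; late has none. Early mean gap = (112 x 3.625 + 42 x 7.25)/154 = 4.6 h, against 7.25 h late, a ratio of 1.57.

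**4. Illustration: a constant effect that decays after delivery.** The documents give no half-life; I assume h = 2 to 24 h. Place the random prompts uniformly in the S = 14.5 h between diaries and let a = S ln2 / h. The mean fraction of the effect left at the second EMA is:

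- one random prompt a day: (1 - e^-a)/a
- three random prompts a day: 3[1/a - 2/a^2 + 2(1 - e^-a)/a^3]

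| Half-life | Left, weeks 2-5 | Left, weeks 6-14 | Late/early | Apparent loss |
|---|---|---|---|---|
| 2 h | 0.406 | 0.198 | 0.49 | 51% |
| 4 h | 0.591 | 0.366 | 0.62 | 38% |
| 8 h | 0.751 | 0.569 | 0.76 | 24% |
| 24 h | 0.903 | 0.817 | 0.90 | 10% |

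Simulation with prompts spread one per equal segment of the day, and with 80% completion, gives late/early ratios of 0.49-0.57, 0.62-0.65, 0.76-0.77 and 0.90-0.91. These figures are for a split at week 5/6. For weeks 2-8 versus 9-14, late/early becomes r/(0.727 + 0.273r), where r is the ratio in the table. The apparent loss is then about 43% at 2 h and 7% at 24 h.

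**5. What this does not size.** Step 4 concerns the mean message effect. The planned score is the share of pairs with a drop of at least one point. Pairs start at high-risk moments, and a longer gap may also allow more spontaneous drops, which count as successes.

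**The case against.** Several points on the other side are sound.

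- Early and late are undefined. A split lying wholly within weeks 2-5 or wholly within weeks 6-14 would avoid the schedule change. That stands, but the plan does not say this, and a split of the whole pair window cannot avoid it.
- The preceding sentence compares success scores between conditions, so a QuitGuide contrast may be intended. It would largely remove the natural course of withdrawal, since both arms complete EMAs. It would not remove the lag problem: the message effect would still be read about twice as late after week 5.
- Participant-initiated EMAs shorten some gaps; an About to Slip EMA is followed up 15 minutes later. So doubling is exact only for the mean scheduled within-day gap.
- This is an additional analysis of an alternative Aim 2 score.

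A reader might infer more than the documents support. Putting the mean gaps straight into a 4 h half-life gives 2^(-7.25/4) / 2^(-3.625/4) = 0.285/0.534 = 0.53, an apparent loss of 47%. That ignores the spread of prompt times; averaging over it gives 35% to 38%. The statement that the risk estimator "identified 80% of all smoking lapses within 4 hours of the lapse" describes a detection window and says nothing about how long a message acts. Nor do day-long gaps in weeks 15-27 belong here, because section E places the pairs in weeks 2-14.

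**Conclusion.** The concern holds in limited form. As written, the comparison can give a wrong answer about waning, because any split of weeks 2-14 changes the measurement lag along with the period. That the mean scheduled gap doubles follows from the protocol; 1.7 to 2.0 times covers missed prompts and overnight pairs. An apparent fall of roughly 10% to 50% in the mean effect rests on an assumed half-life of 2 to 24 h, a 16-hour day and a split at week 5/6; a later split gives somewhat less. A reader might conclude that the analysis is bound to show false habituation. The documents do not support that: spontaneous drops count as successes, so the net direction for the success percentage is unknown. The withdrawal part applies only if no contrast with QuitGuide is made, and the plan does not state one. The primary abstinence analysis is not affected.

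**What to change.** Define early and late in the plan, and test change over time as the arm-by-period interaction (Smart-T minus QuitGuide, late versus early). Fit it in a pair-level mixed model restricted to same-day pairs in weeks 2-14. Include hours between the two EMAs and the interaction of hours with arm. Hours as a main effect alone would not do, because it is the message effect, the difference between arms, that may shrink with lag. Prespecify the form of the hours term. As a sensitivity analysis, report the trend within each constant-schedule block, weeks 2-5 and weeks 6-14 separately.

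The cost is analysis wording and a slightly more complex model; the time stamps already exist. The within-block trends are less precise. On the plan's 80%, 25% and 25% assumptions, weeks 2-5 give 112 x 0.05 = 5.6 pairs per message type per participant and weeks 6-14 give 126 x 0.05 = 6.3. Two-week blocks such as weeks 2-3 versus 4-5 would leave only 2.8 each and would largely give up the question of change over the study. For that reason the within-block trends should support the main model and not replace it.

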#### **F. Gender/Minority/Pediatric Inclusion for Research**

**Inclusion of Women and Minorities.** The study has no inclusion/exclusion criteria based on gender or race/ethnicity. However, QDS and EMA data collection software is currently offered in English only; therefore, all participants must be able to read English at > 6th grade level. Based on historical data from TTRP patrons, study participants are expected to be 59% White, 25% Black, 10% American Indian, 6% other race, 3% Hispanic, 61% female, and 45% will report < \$20,000 in yearly household income. No eligible participants will be excluded from this study due to gender, race, or ethnicity. We will continuously monitor enrollment in order to ensure that we are meeting recruitment goals to avoid under-recruiting minorities. If the enrollment for minorities is lower than expected, we will make special efforts to increase participation by advertising in community newspapers, local church organizations, and community centers. We expect that intervention groups (i.e., Smart-T and QuitGuide) will be similar in baseline characteristics (e.g., sex, race/ethnicity) due to randomization; however, in addition to the chi-square analysis, we will perform logistic regression to determine if the odds of abstinence vary by baseline characteristics (e.g., sex, race/ethnicity). We will examine the interaction between treatment condition and sex (and race) to identify potential differential effects on abstinence. Finally, we will examine the interaction between Smart-T message type and sex (and race) to identify potential differential effects on lapse risk factors.

**Inclusion of Children.** Services provided by the TTRP (the proposed data collection site) are available to any person ≥ 18 years of age. Children < 18 years of age do not receive services at the TTRP (they are referred to the Oklahoma Tobacco Helpline) and will not be included in this study for several reasons. First, in order to include these children, the assessment protocols being tested would require significant modification to take into account their differing cognitive and psychosocial development. Making these modifications would result in a fundamentally different set of tasks and would essentially necessitate the conduct of two different studies. We do not consider this feasible, short of submitting two different grant applications. Second, the FDA has not approved the use of over the counter nicotine replacement therapy in children under the age of 18, so we would not be able to provide the full treatment to those individuals, making the use of the protocol less than ideal and no longer state-of-the-art. Third, modal quit behavior for smoking occurs in adulthood, making this developmental time period particularly well suited to a test of mediating processes during a smoking cessation intervention.

## **G. Human Participants**

**1. Subject Population.** Participants (N=450) will be recruited through the TSET Health Promotion Research Center (HPRC) Tobacco Treatment Research Program (TTRP). Participants will also be recruited through advertisements (e.g. Facebook and Craigslist ads). Those who respond to study advertisements will complete a brief REDCap screener online (i.e., OKSmokerstudy.com), and those who qualify for the study will be contacted by study staff and scheduled for a screening/baseline process. Interested individuals may be included in the study if they: 1) demonstrate > 6th grade English literacy level (i.e., phone based EMAs require >6th grade literacy; at least 88% of all individuals screened for our previous EMA studies have met this inclusion criterion), 2) are willing to quit smoking 7 days from the Baseline process, 3) are  $\geq 18$  years of age, 4) have an expired carbon monoxide (CO) level  $\geq 7$  ppm suggestive of current smoking, or substantiate smoking status (e.g., send picture of their pack of cigarettes) during the remote baseline process conducted via phone, 5) are currently smoking  $\geq 5$  cigarettes per day, 6) are willing and able to complete the 27 week follow-up session over the phone and via EMA, 7) are willing and able to complete EMAs and CO tests on their personal smartphone (those who use their personal smartphone will receive an additional \$15 per month to offset data plan costs if at least 50% of assessments are completed and contact details are confirmed) or a study provided smartphone, 8) have household income  $\leq 200\%$  of the federal poverty guideline, 9) have no contraindications for over the counter nicotine replacement therapy (i.e., individuals with uncontrolled blood pressure, history of myocardial infarction within the past two weeks, or current pregnancy or plans to become pregnant during the study period will be excluded).

**2. Sources of Research Material.** All data collection will follow HIPAA guidelines. There will be 3 sources of data for the current study: 1) in-person or call based data collected during the baseline process. The Remote Baseline process will occur via phone calls with research staff, and Baseline data will be primarily collected via REDCap surveys, 2) EMA data collected on study-provided or personal smartphones via the encrypted Insight™ smartphone application, and 3) expired carbon monoxide data assessed via Vitalograph ecolyzer (Baseline visit only) and Bedfont iCO smokerlyzer (Baseline and EMA). Measurements of height and weight will be collected at the baseline visit.

**3. Recruitment and Informed Consent.** Individuals seeking smoking cessation treatment during their first TTRP visit will be approached by study research staff to discuss this study. Participants will also be recruited through advertisements (e.g. Facebook and Craigslist ads). All study staff have completed training in the ethical conduct of research (including CITI training). Prior to screening, potential participants will receive information about this voluntary study and will be informed that TTRP services are not contingent upon study enrollment. Those who remain interested in participating will be provided detailed information about the study by research staff, given the opportunity to have their questions answered in a private room or in phone calls, and will complete written informed consent via paper or REDCap. Remote participants will review and sign consent forms electronically via a REDCap link, and will be provided a copy for their records.

**4. Risks.** Participation in this study poses minimal risk to participants. Potential risks include loss of confidentiality, coercion related to compensation for completion of study assessments, nicotine withdrawal, and side effects from nicotine replacement therapy. Each of these risks are discussed below. The consent form will clearly describe the potential risks of this study. Thus, participants who feel uncomfortable with such assessments or intervention programs are not likely to agree to participate.

*Loss of confidentiality.* One potential risk is loss of confidentiality. The severity of harm in the case of loss of confidentiality may range from mild to severe depending upon the individual and the specific circumstances. However, the risks of participation in the study are similar to that of participation in usual in person or phone based smoking cessation treatments, as loss of confidentiality may be experienced in each case. Other possible adverse events might include compromised data security and discomfort related to being asked study questions. The research team will monitor risk and report adverse events immediately to the IRB. Because sensitive data will be collected, a Certificate of Confidentiality will be obtained prior to the onset of data collection to ensure that data cannot be subpoenaed and used against participants in court, and this information will be explained to all participants during the informed consent process (Certificates of Confidentiality are now automatically granted for all NIH grants).

*Compensation and Potential for Coercion.* Considering the very low-income levels of the anticipated study sample, we are aware of the potential for coercion in this study due to the provision of subject payments. We have paid particular attention the size of payments, considering the effort required to complete study assessments. Participants will receive a \$30 gift-card for completing the baseline assessment and \$50 gift-card for completing the 26-week post-quit assessment (those who complete the final longer EMA within 24 hours will receive a \$5 bonus payment) and qualitative interview at either the 16-week mark or the 26-week mark. Participants will only be asked to complete 1 qualitative interview and will not be asked to complete both interviews. We will ask all participants to complete interviews until we have completed 30 16-week interviews and a combined 200 26-week interviews (100 per group). In addition, participants will receive compensation based upon the percentage of EMAs that they complete each month. Participants will be able to earn a maximum total of \$624 in gift cards over 27 weeks (average of < \$20/week).

*Nicotine Withdrawal.* There is a strong likelihood that most study participants who quit smoking will experience some nicotine withdrawal symptoms, including anxiety, restlessness, anger, irritability, sadness, problems concentrating, appetite change and weight gain, insomnia, and decreased heart rate. Withdrawal symptoms are usually short-lived, with most symptoms abating within 1-2 weeks. Importantly, Drs. [name] and [name] are trained and experienced in addressing these issues as they emerge and the research team will be trained and supervised in the monitoring and addressing of psychological problems.

*Nicotine Replacement Therapy (NRT; Patch and Gum/Lozenge).* Nicotine patch and gum/lozenge are smoking cessation medications that are available over the counter and side effects (e.g., nausea, skin irritation) are generally mild. All participants will receive NRT. NRT has been shown to increase successful smoking cessation, and is currently offered via Quitline via mail in all but 5 states. Consistent with over-the-counter package labeling, participants will be offered up to 10 weeks of nicotine patches (i.e., label dosage recommendations will be followed) and up to 12 weeks of nicotine gum or lozenges (i.e., participants will receive a 4 week supply of NRT at the baseline visit and will be mailed NRT upon request for post-quit weeks 5-12). After 12 weeks, pharmacotherapy will be discontinued. Participants will be asked if they experienced NRT side effects each day via EMA. If/When participants report severe side effects, the app will suggest that the participant call 911. In addition, the app will automatically send an encrypted email to study staff when severe side effects are reported. Study staff will attempt to contact the participant to discuss these side effects.

*Alternative Treatments.* The consent form will explain that, rather than participating in this study, individuals may choose to enroll in the standard Tobacco Treatment Research Program (TTRP) which provides free smoking cessation medications and in-person, or phone-based smoking cessation counseling.

